Analysis for Aim 1: Analyses will be performed according to the principle of intention-to-treat. including all randomized drivers. Unless otherwise specified, hypothesis tests will be two-sided with alpha=.05, with 95% confidence intervals or p values reported. All canalyses will be performed using SAS/STAT® software. First, descriptive statistics will be computed for baseline patient characteristics, initially testing for differences between control and intervention groups (including for key covariates, Table 3.3). We will assess site effects by comparing demographic variables across the sites, using ANOVA for continuous measures and chi-square tests of proportions for categorical measures. If no statistically significant differences exist among sites. we will ignore site and formally test the differences in proportions or means as described below. If there are significant differences among sites, then (assuming enough events) we will use separate bivariate logistic regression models for each aim described below, with a fixed effect for site and with treatment arm as the main predictor. For longitudinal analyses, we will conduct logistic regression with unstructured correlation of generalized estimating equations (GEE) to account for the repeated observations for each participant. Statistical significance will be evaluated at one-sided p<.05 level. Analyses of the DDA's longitudinal effects may be vulnerable to bias, as control arm participants may be exposed to intervention arm messages through exposure to available materials or courses related to driving safety or cessation (e.g., websites, physician counseling, AARP courses). We will assess exposure to other sources of information through structured questions. To mitigate the impact of this potential bias, we will adjust measurements of contamination as applicable. In all analyses, validation of distributional and parameterization assumptions will be checked and data transformations (e.g. logtransformations) or alternative methods will be implemented as appropriate.

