Aim 1b. Test the DDA's longitudinal effect on psychosocial outcomes at 12 and 24 months. Hypothesis 1b: Participants in the DDA group will have reduced prevalence of depressive symptoms and of decision regret but maintained life space, at 12 and 24 months after enrollment, compared to control participants. We will use descriptive statistics, including proportions with 95% CIs or medians and interquartile ranges, for comparison between treatment groups. We will utilize GEE with a linear link, and a linear mixed model (LMM) with a random intercept, fixed effects and a linear link for each outcome. We will adjust for baseline characteristics (gender, age, education, etc.), driving behaviors and other variables. We will perform sensitivity analyses to examine the missing assumption under maximum likelihood.

Aim 1c. Test the DDA's longitudinal effect on driving behaviors at 12 and 24 months. Exploratory: The DDA does not provide specific recommendations as to whether the participant should stop driving or not. We will compare the proportion of participants who change their reported driving behaviors (reduce driving or cease altogether) over the follow-up period to examine whether the DDA appears to affect them. We will apply GEE with a logistic link, and a generalized LMM (GLMM) with a random intercept and a logistic link for each outcome. Also, we will adjust demographic variables and appropriate variables.

Secondary analyses: Secondary analyses by gender will be conducted, as we hypothesize there will be differences in behavior and outcomes based on gender, and the belief that the responses to DDA intervention may be heterogeneous between men and women. Aim 1a-1c will be considered gender analyses using logistic regression and GLMM. We will also examine the degree of concordance (or discordance) within driver-family dyads on various measures, including DCS and current versus desired level of family involvement in driving retirement process (part of the driving questionnaire). For longitudinal data, we will examine changes across time points (follow-up at 6, 12, 18, 24 months) and correlation between older driver and family member report.

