Secondary analyses: Additional analyses will include dichotomizing groups based on insight into cognitive function, using the Beck Cognitive Insight Score and following procedures outlined in Aim 2a. We will also examine trajectories of attitudinal readiness to stop driving over time; this will be the first longitudinal study of ARMT scores, and we suspect scores will ultimately decrease (indicating greater readiness for driving retirement) but may first increase (as drivers cope with feeling threatened or worried about the transition). Employing an exploratory trajectory analysis to the data (rather than a recurrent cross-sectional approach) allows us to focus on changes over time for each individual. By following individual trajectories, we are likely to observe factors influencing individuals' decisions rather than have these factors obscured by focusing on recurrent cross-sections of the data. Data will be organized as time-ordered,

AUTO Study Protocol: Version Date: 12/22/21 PI: [name], MPH COMIRB No: 19-0059 sequential matrices (one matrix per unit of analysis). Descriptive statistics for the ARMT scores will be summarized at each time point. In addition, study participants will be grouped into subcategories based on the type of trajectory (both shape and scale) being observed. Intervention group status and its effect on trajectory will be formally explored. Other variables of interest will be assessed in an exploratory manner. Additional secondary analyses will examine interactions between personality factors, ARMT, and the DDA. We will also explore the effect of gender, recognizing that women are more likely than men to self-regulate driving and to stop driving sooner.

**Analysis for Aim 3**: In a mixed-method study with key stakeholders (drivers, family members, healthcare providers, and experts in the field), we will inform future DDA testing and eventual implementation.

Aim 3a. Explore acceptability of the DDA, including recommended modifications.

Aim 3b. Explore views on the ideal settings for DDA use (e.g., clinical setting versus community program). For these qualitative data, we will use a team-based, mixed inductive-deductive approach to review and code transcripts, identify dominant themes, compare themes across content areas, and then group these themes or create sub-themes. We will use "member-checking" to discuss final themes and theme organization with key informants.

Figure 3.

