**Longitudinal follow-up:** Participants will be contacted for telephone follow-up at pre-specified intervals (6, 12, 18, and 24 months after initial visit for drivers; 12 and 24 months after initial visit for study partners). Participants will be contacted via phone call, text message, or email (depending on participants' preference) to schedule the follow-up interviews. For these follow-up interviews, the RA will contact the participant at the participant's preferred phone number at a mutually-convenient time. Trained RAs across sites will follow COMIRB policies regarding contacting participants for follow up. Per suggested guidelines, participants will be contacted at least three times, but no more than 10 contact attempts will be made. Additionally, staff will attempt to reach the participant at different times of the day, leave a brief message on second attempt followed by a more detailed message on third (for participants who elect to receive reminders by phone call), and will reach out by email and/or text message as needed/as

AUTO Study Protocol: Version Date: 12/22/21 PI: [name], MPH COMIRB No: 19-0059 preferred. Follow-up questionnaires will be administered via phone by RA unless the participant strongly prefers to complete an in-person interview. During follow up, participants will repeat all psychosocial and decisional measures. The study team will access participants' driving records for the past 12 months before enrollment and again up to every 12 months after enrollment.

**Aim 3 Recruitment:** For providers, study recruitment will include flyers posted in staff work areas and up to 3 emails to eligible providers, asking interested providers to contact study staff for further description of the study and scheduling of an interview. For experts, we will send up to 3 emails and describe the study in greater detail to interested respondents. For the older drivers and family members/study partners, at the end of the 24 month interview we will ask participants if they are interested in being contacted with information about the interview opportunity. Study staff will follow-up with these interested participants via phone or email, depending on the participant's preference.

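### The Aim 1b mixed model has a random intercept only, so its model-based standard errors for some 24-month and change contrasts depend on an untested equal-variance, equal-correlation assumption

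*Combined protocol and SAP*

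**What the plan says.** The Aim 1b paragraph of Outcome Measures and Analysis names two models for depression, decision regret and life space. The first is a GEE: "We will utilize GEE with a linear link". The second is "a linear mixed model (LMM) with a random intercept, fixed effects and a linear link for each outcome". It does not say which is primary, how time enters, whether the baseline value of the outcome is a covariate, or which standard errors are used. No random slope, residual covariance structure or robust standard error is named for the mixed model.

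Analysis for Aim 1 asks, for longitudinal work, for "unstructured correlation of generalized estimating equations (GEE) to account for the repeated observations for each participant". That sentence is worded for logistic regression. The same paragraph says that in all analyses "validation of distributional and parameterization assumptions will be checked" and that "alternative methods will be implemented as appropriate".

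Hypothesis 1b concerns 12 and 24 months. Under Longitudinal follow-up, contacts are at "6, 12, 18, and 24 months after initial visit for drivers".

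**The concern.** A random intercept with independent residuals (the ordinary reading of the text) is compound symmetry. Two visits 6 months apart are taken to be as correlated as two visits 18 months apart, and the variance at 24 months is taken to equal that at 6 months. The longitudinal GEE is allowed a free correlation matrix; the mixed model is not.

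If compound symmetry is false, the mixed model's own standard errors are wrong for some contrasts, in a direction that depends on the contrast. The GEE and the mixed model could then give different p values for the same hypothesis for a purely technical reason, and the plan has no rule for choosing between them.

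**Working it through.** **No plan figure to reproduce.** The documents give no variance, correlation, standard error or power for Aim 1b. The sample-size calculation (300 drivers, 150 per arm, 90% power) is for Aim 1a. Every covariance below is an assumption.

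**Method.** Let S be the true covariance of the four follow-up visits. On balanced data a random-intercept fit replaces S by M, with v (the mean of the diagonal of S) on the diagonal and c (the mean of the off-diagonal entries) elsewhere. For a contrast x between arms, let R = x'Sx / x'Mx; arm size cancels. Two-sided error is 2 × [1 − Φ(1.96/√R)].

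**Case 1: correlation ρ per 6 months, decaying as a power of ρ, with variance 1 throughout.** For ρ = 0.8, c = (3×0.8 + 2×0.64 + 0.512)/6 = 0.6987.
- 24-month arm contrast, categorical visits: model 1, true 1, R = 1, error 5.0%. The 12-month contrast is the same.
- 6-to-24-month change: model 2(1 − 0.6987) = 0.603, true 2(1 − 0.512) = 0.976, R = 1.62, error 12.4%.
- 18-to-24-month change: model 0.603, true 2(1 − 0.8) = 0.400, R = 0.66, error 1.6%.
- Arm-by-linear-time, weights (−0.3, −0.1, 0.1, 0.3): R = 1.84, error 14.9%.

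| Contrast | ρ = 0.6 | ρ = 0.8 | ρ = 0.9 |
|---|---|---|---|
| 12 or 24 months, categorical visits | 5.0% | 5.0% | 5.0% |
| Change 6 to 24 | 10.3% | 12.4% | 13.4% |
| Change 12 to 24 | 7.1% | 7.3% | 7.3% |
| Change 18 to 24 | 2.2% | 1.6% | 1.4% |
| Arm by linear time | 12.5% | 14.9% | 16.0% |
| 24 months, linear time | 7.2% | 6.5% | 5.8% |
| 24 months, categorical visits, baseline outcome as covariate | 6.7% | 8.9% | about 10% |

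**Case 2: drivers differ in slope.** Intercept variance 0.6, residual variance 0.4, and slope variance s per 6-month step squared, with intercept and slope uncorrelated.
- s = 0.02: variances 1.02, 1.08, 1.18, 1.32; v = 1.15. At 24 months R = 1.32/1.15 = 1.148, error 6.7%. At 12 months R = 1.08/1.15 = 0.939, error 4.3%.
- s = 0.06: variances 1.06, 1.24, 1.54, 1.96; v = 1.45. At 24 months R = 1.352, error 9.2%. At 12 months R = 0.855, error 3.4%.
- Slope variance 0.2-0.4 per 24 months squared: error 6.1-7.1% at 24 months and 4.5-4.2% at 12 months.
- Slope variance 0.2 with intercept-slope covariance −0.15: 24-month variance 0.900, v = 0.906, R = 0.993, error 4.9%. The inflation at 24 months is gone.

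**Averaged over visits**, R = 1 in every scenario, because M keeps the average of S.

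**Simulation** (150 per arm, four visits, about 10% monotone dropout, 1,500 runs each; Monte Carlo standard error near 0.6 points):

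| Truth | 24-month contrast, model SE | 6-to-24 change, model SE |
|---|---|---|
| Decay, ρ = 0.8 | 4.8% | 13.3% |
| Decay, ρ = 0.6 | 5.3% | 10.5% |
| Random slope, variance 0.4 per 24 months squared | 7.3% | 6.1% |

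Sandwich standard errors on the same fits gave 4.9-5.2% for the 24-month contrast and 4.9-5.6% for the change.

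**The case against.** The strongest case against has five parts.

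1. **The hypothesis is about 12 and 24 months, and decay does not disturb those contrasts.** This stands for categorical visits and constant variance. A reader might infer that decaying correlation by itself makes the 24-month error bars too small. It does so only if time is linear or the baseline outcome is a covariate, and the plan specifies neither.

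2. **The largest figures belong to tests that the plan does not name for this model.** This stands. A reader might take 12.5-16% as the false-positive rate of Aim 1b, but no slope test is written there. The sentence on changes across time points is under Secondary analyses, and the parallel sentence in the Family member data paragraph uses GEE.

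3. **The documents do not show that these outcomes drift apart.** This stands. The remark about different rates of progress concerns stages of driving cessation. The passage saying that trajectory analysis "allows us to focus on changes over time for each individual" concerns ARMT scores. Neither bears directly on depression, regret or life space, so unequal slopes are plausible but not stated.

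4. **The plan may not use all four visits.** It does not say. With only 12 and 24 months there is one correlation, so decay drops out. Growing variance would still matter: with s = 0.06, v = (1.24 + 1.96)/2 = 1.60, R = 1.225, error 7.7%.

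5. **Safeguards exist.** The GEE is named first and, if it uses robust errors (not stated), is valid for these contrasts. The general clause on checking assumptions could catch the problem. This stands in part: the clause names no covariance check, trigger or replacement, and no model is designated as primary.

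A reader might also infer bias from dropout, because likelihood analysis under missing-at-random relies on the covariance model. No size was established for that, and it is not claimed here.

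**Conclusion.** The point holds in limited form. As written, the mixed model imposes compound symmetry. Under growing variance its error rate for the 24-month contrast is about 6-9%, and a negative intercept-slope covariance can remove that excess. Under decaying correlation the stated 12- and 24-month contrasts are sound with categorical visits. Long-span change and any linear-time test are not, and adjacent-visit changes err the other way.

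These sizes rest on assumed covariances, four visits, model-based standard errors and a two-sided 0.05 level. Analysis for Aim 1 also mentions a one-sided 0.05 level, under which the figures would differ. The outcomes are secondary and the primary Aim 1a analysis is untouched. The documents do not support a claim that the Aim 1b results as a whole would be invalid.

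**What to change.** In the Aim 1b paragraph, replace the random intercept in the linear mixed model with an unstructured within-driver covariance over the 6, 12, 18 and 24 month visits. Enter visit as a categorical factor, use small-sample degrees of freedom, and take the 12- and 24-month arm contrasts from this model. If it does not converge, keep the simpler model and use sandwich standard errors.

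The cost is one phrase in the plan and one line of SAS code. Four visits need 4 variances and 6 covariances, 10 parameters against 2 now, which about 300 drivers can support. The unstructured model remains valid if compound symmetry turns out to be true.

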## AUTO Study Protocol: Version Date: 12/22/21 PI: [name], MPH COMIRB No: 19-0059 **Table 3. Key study measures**. Shown in relation to measurement point (pre- or post- DDA or website

Participant, and analytic plan. • = about self,  $\circ$  = as surrogate about older driver

		[name]/friends			Analytic Plan				
Domaiı	n and Key Measures	En	roll	F/u	Enr	oll	F/u			
		Pref	Post		Pre	Post			Hypoth.	Scoring
Immediate outcome										
Decision Conflict	Decisional Conflict Scale (DCS)	•	•	•	٠	•	•	1° Outcome	1a, 2a, 2b, 2c	Score <25
Knowledge	Knowledge questionnaire	•	•	•		•	•	2° Outcome	1a	Descriptive (cat.)
Values concordance	DCS Values Clarity subscale	٠	٠	•	٠	٠	٠	2° Outcome	1a	Descriptive (cat.)
Self-efficacy	Decision Self-Efficacy scale	•	•	•		•	•	2° Outcome	1a	Descriptive (contin.)
Longitudinal outcome										
Depression	PROMIS depression	٠		٠				2°	1b	T-score >50
								Covariate	1c	Descriptive (contin.)
Decision regret	Ottawa Decision Regret Scale			•			•	2° Outcome	1b	Descriptive (contin.)
Life space	Life-Space Assessment	٠		•			0	2° Outcome	1b	Descriptive (contin.)
Driving behaviors	Amount; reduction or cessation	•		•			0	2° Outcome	1c	Descriptive (cat.)
Subgroups										
Cognitive	5 minute MoCA			٠			•	Eligibility		Score ≥21
screening								Covariate	•	
Cognitive function	BTACT, OTMT	•						Stratify	2a	Normal vs. impaired
Insight	Beck Cognitive Insight Scale	٠		٠				Stratify	2a	R-C index ≥3
Decisional capacity	SPACED	•		•				Stratify	2b	# correct answers
Attitudes about	ARMT	٠		٠				Stratify	2c	Mean score ≥3.57
anning								Covariate	1c	_0.07

	Drivers	Family/fri	Analytic Plan				
Domaii	n and Key Measures	Enroll F	/u Enroll	F/u			
		PrePost	Pre Post			Hypoth.	Scoring
Other covariates							
Demographics	E.g., age, gender, race/ethnicity, marital/home status, education, income, urban/rural	•	• •	•	Covariate	all	Descriptive (cat.)
Physical health	Medical history, Activities of Daily Living, PROMIS global health	•	•	•	Covariate	all	Descriptive (cat.)
Mental health	PROMIS Emotional Support, Social Isolation; Perceived Stress Scale	•	•		Covariate	1b, 1c	Descriptive (cat.)
Personality	TIPI	•			Covariate	1c, 2c	Descriptive. (cat.)
Driving behaviors	Crashes, self-driving technologies	•	•	0	Covariate	1c	Descriptive (cat.)
Driving resources	Alternative transportation, support	•	••	• 0	Covariate	1c	Descriptive (cat.)
Driving education	Use of websites, courses, or other material driving or cessation	•	• •	•	Covariate	1c	Descriptive (cat.)

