**Randomization**: At each site, enrolled drivers (with their family members) will be randomly assigned in equal numbers to the DDA or control arm (Figure 4). To reduce bias and aim for balance among arms, we will randomize patients in blocks with randomly varied block sizes of 4 and 6. While RAs delivering the intervention to patients cannot be blinded to treatment, we will conceal allocation using a centralized, computer-generated list that RAs will access only after enrollment. Other study staff, including a different RA (whenever possible) doing follow-up calls, will be blinded to study arm.

**Baseline Measurements & Intervention**: The driver and family member will be randomized to the same arm but will complete all study measures and interventions separately from each other. For each participant (including those enrolled in person as well as those enrolled remotely by phone), the RA will use a study tablet or laptop to administer the introductory questionnaire (Figure 4, Table 3). In the intervention arm, participants will then complete the web-based DDA; control group participants will be directed to the NIA "Older Drivers" website. After completing the DDA or website review, all participants in both arms will answer questions about their knowledge, values, and plans related to driving cessation (Table 3). For family members, questions will generally be about the older driver, though there will be specific questions concerning their relationship, frequency of contact, and possible co-dependence for transportation. Whenever possible, participants will receive a printed handout of either their DDA results or the NIA webpage (for those enrolled in person) or will receive instruction from the RA about how to save an electronic copy of the DDA results or the NIA webpage (for those enrolled in person) or the NIA webpage (for those enrolled remotely by phone).

**Identifying driving risk**: At the request of the DSMB, the study team will use American Academy of Neurology (AAN) guidelines to identify drivers who are at moderate risk for being unsafe to drive (https://www.aan.com/PressRoom/home/GetDigitalAsset/8471). Per AAN

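### The Aim 1b models for depression and life space do not prespecify use of the outcome's own enrolment score, although both scores are collected before exposure

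*Combined protocol and SAP*

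**What the plan says.** Under Outcome Measures and Analysis, Aim 1b is set out as: "Test the DDA's longitudinal effect on psychosocial outcomes at 12 and 24 months". The models are described so: "We will utilize GEE with a linear link, and a linear mixed model (LMM) with a random intercept", with fixed effects, for each outcome. The covariate sentence is "We will adjust for baseline characteristics (gender, age, education, etc.), driving behaviors and other variables".

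In Table 3, the longitudinal rows "PROMIS depression" and "Life-Space Assessment" are marked for drivers at enrolment and at follow-up. The Ottawa Decision Regret Scale is marked at follow-up only. Depression is an outcome for 1b and a covariate for 1c. Life space appears only as an outcome.

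The order of procedures is in Study Design and Research Method, Baseline Measurements & Intervention. The introductory questionnaire comes first, and after it: "In the intervention arm, participants will then complete the web-based DDA; control group participants will be directed to the NIA" website. The enrolment scores therefore precede exposure in both arms.

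No text states how the enrolment depression or life-space score enters the Aim 1b models.

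**The concern.** The earlier value of a repeated score is usually its strongest single predictor. If it is left out, differences between drivers that existed before exposure stay in the residual, and any chance imbalance at enrolment passes into the 12- and 24-month contrasts.

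The wording leaves three analyses open, and they differ in efficiency: ignore the enrolment score, condition on it, or treat it as another response row. With the list open-ended, that choice could also be made after the data are seen. Aim 1b carries the trial's claim about the psychosocial consequences of reduced driving, so its models should be fixed in advance.

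**Working it through.** **The plan's own figure.** The only stated sample size for drivers in Aim 1 is for Aim 1a: 150 per arm, 90% power, 0.05, 10% loss, for a difference of 20 points or more in the proportion with DCS below 25. The text does not give the underlying proportions, so take two examples.
- 40% against 60%: n = [1.96·√(2·0.5·0.5) + 1.2816·√(0.24 + 0.24)]² / 0.20² = (1.386 + 0.888)² / 0.04, or 130 per arm. Then 130/0.9 gives 145.
- 50% against 70% with continuity correction: 134 per arm. Then 134/0.9 gives 149.

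The stated 150 is reproduced. There is no corresponding figure for Aim 1b.

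**Inputs for Aim 1b**
- From the Sample Size section: 150 per arm less 10% = 135 per arm.
- From Analysis for Aim 1: "Unless otherwise specified, hypothesis tests will be two-sided with alpha=.05". A one-sided 0.05 level is stated after the longitudinal GEE sentence, so both are run.
- From the Depression paragraph: PROMIS T-score SD of 10.
- Assumed, not in the documents: a continuous score at one time point; 80% power for the model without the enrolment score (90% also shown); and a correlation ρ between enrolment and follow-up, net of the other planned covariates, of 0.3 to 0.7.

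**Formula.** The reference noncentrality is 1.96 + 0.8416 = 2.8016. The corresponding difference is 2.8016·√(2/135) = 0.341 residual SD, which is about 3.4 T-score points if the other covariates explain nothing. Conditioning on the enrolment score multiplies the variance by 1 − ρ², so power = Φ(2.8016/√(1 − ρ²) − 1.96). If enrolment is instead an unconstrained response row, the arm-by-time contrast against enrolment is a change-score comparison with variance factor 2(1 − ρ).

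| ρ | 1 − ρ² | Power, enrolment as covariate | 2(1 − ρ) | Power, change-score contrast |
|---|---|---|---|---|
| 0.3 | 0.91 | 83.6% | 1.40 | 65.8% |
| 0.5 | 0.75 | 89.9% | 1.00 | 80.0% |
| 0.7 | 0.51 | 97.5% | 0.60 | 95.1% |

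The difference detectable with 80% power falls from 0.341 SD to 0.341·√0.75 = 0.295 SD at ρ = 0.5, and to 0.341·√0.51 = 0.244 SD at ρ = 0.7.

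**Sensitivity at ρ = 0.5**
- From 90% reference power: Φ((1.96 + 1.2816)/√0.75 − 1.96) = 96.3%, a gain of 6.3 points.
- One-sided 0.05 from 80%: Φ((1.645 + 0.8416)/√0.75 − 1.645) = 89.0%, a gain of 9.0 points.
- Mean of two follow-up visits with a common correlation of 0.5: the variance falls from 0.75 to 0.50, and power rises from 80% to Φ(2.8016·√1.5 − 1.96) = 92.9%.

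**The case against.** A reader might infer that the Aim 1b models leave the enrolment score out. The text does not go that far. The covariate list is open at both ends, and an enrolment score is itself a baseline characteristic.

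Nor does Table 3 settle it. One could argue that depression is assigned as a covariate to 1c only, and life space to none, so both are excluded from 1b. But Table 3 assigns driving behaviors only to 1c, while the Aim 1b paragraph adjusts for them. Table 3 is therefore not a complete list of 1b covariates, and absence from it proves nothing.

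The repeated-measures model could also use the enrolment score as a response. With arm means constrained equal at enrolment, this recovers essentially the same precision as the covariate. The plan does not say so, and an unconstrained row gains nothing at a correlation of 0.5 and loses power at 0.3.

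The planned covariates may already absorb part of the gain. Table 3 assigns emotional support, social isolation and perceived stress to 1b, and daily activities and global health to all hypotheses. That is why the correlation above is taken net of them. If it is only 0.3, the gain from 80% is about 4 points.

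Depression may be analysed as a binary outcome. Table 3 scores it as a T-score above 50, Hypothesis 1b refers to prevalence, and Analysis for Aim 1 mentions logistic GEE, whereas the Aim 1b paragraph gives a linear link. The variance factor does not carry over to a dichotomised score.

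Finally, omission would not bias a randomised comparison, and Hypothesis 1b judges life space against control, so it can be interpreted between arms. The plan also tests for baseline differences, but it does not say what the 1b models would do with the result. All of this limits the size of the point. It does not supply the missing specification.

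**Conclusion.** The point holds as a gap in specification: two pre-exposure scores are collected, and their role in the models for the same outcomes is not stated. What is at stake is precision and protection against chance imbalance in secondary outcomes; the primary analysis is not affected.

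A reader might take a loss of about 10 points of power as established. It is not. That figure needs a net correlation of 0.5 and 80% power without the enrolment score, and neither is in the documents. Under two-sided 0.05 from 80%, the gain runs from about 4 points at 0.3 to 17.5 at 0.7. At 0.5 it is about 6 points from 90%, and about 9 from 80% under one-sided 0.05. The figures apply to life space, and to depression only if it is analysed as a continuous T-score. Decision regret is outside the point.

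**What to change.** Under Aim 1b, state that each model for PROMIS depression and for life space takes the follow-up values, including 12 and 24 months, as the response; has arm, time and arm-by-time as fixed effects; and includes the enrolment score of the same measure as a fixed-effect covariate. An acceptable alternative is to carry enrolment as a response with arm means constrained equal at that visit; choose one in advance. Add matching 1b covariate entries for enrolment depression and enrolment life space to Table 3.

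The cost is one sentence and a table edit. No new data are needed, and the covariate version uses one degree of freedom per model.
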